6. INVESTIGATIONAL MEDICINAL PRODUCT

6.1 Dose and Schedule of IMP and Comparator(S)

Erlotinib will be administered as single daily oral dose of 150 mg, until disease progression or unacceptable toxicity. No dose escalation of erlotinib is permitted. Dose reduction will be allowed according to protocol (Section 6.1.).

Dose Modifications, Interruptions and Delays

Reduction of dosing for adverse events may take place at any time during the study.

Diarrhoea and skin rash are the major side effects associated with erlotinib. Other known side effects, include dry skin, fatigue, pruritus, nausea, vomiting, anorexia, abdominal pain,

gastrointestinal perforation, dry mouth, dry eye, and headache. Dose reductions can be made according to the system exhibiting the greatest degree of toxicity. All toxicities will be graded according to the NCI CTC-AE version 4.0.

In the event of toxicity (e.g., diarrhoea, rash) that is not controlled by optimal supportive care, or not tolerated due to any reason, regardless of severity, the daily dose of erlotinib will be decreased to 100 mg/day.

Within 2 weeks following a dose reduction, erlotinib related toxicity must improve by at least one NCI-CTC grade and be NCI-CTC Grade 2 or better (any ocular toxicity must improve to NCI-CTC Grade 1), or a further dose reduction to 50 mg/day will be required.

Table 3 - Dose Level Reductions

Starting Dose	First reduction	Second reduction
150 mg/day	100 mg/day	50 mg/day

Patients who cannot tolerate a dose reduction to 50 mg/day will be permanently discontinued from the study.

Dosing may be interrupted for a maximum of 2 weeks if clinically indicated and if the toxicity is not controlled by optimal supportive medication.

Once a patient has had a dose reduction for toxicity, the dose will not be re-escalated except in the case of erlotinib related rash. In the event of a rash, dose can be re-escalated when rash is NCI-CTC Grade 2.

Supportive Care Guidelines

Diarrhoea:

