Diarrhoea has been commonly observed (~ 50% patients) and is usually transient in nature. Previous trials have shown that the frequency and severity of diarrhoea rarely hindered administration of erlotinib and could be managed with loperamide. The recommended dose is loperamide 4 mg at first onset, followed by 2 mg every 2 – 4 hours until diarrhoea-free for 12 hours. Patients with diarrhoea should have regular monitoring of their electrolytes and be adequately rehydrated (see table 2 below). Prophylactic use of anti-diarrhoea treatments is not advised.

Table 4 - Guidelines for management of erlotinib-related toxic effects:

Toxicity	Grade	Guideline for management	Dose modification of erlotinib*
Keratitis	2	Interrupt the treatment. Ophthalmologic assessment.	Hold until recovery, and then restart at reduced dose. Continue regular ophthalmological assessments while on treatment.
	≥ 3	Discontinue treatment and seek ophthalmological advice	
Diarrhoea	1	Consider Loperamide (4 mg at first onset, followed by 2 mg every 2 – 4 hours until diarrhoea free for 12 hours) and appropriate rehydration.	None
	2	Loperamide (4 mg at first onset, followed by 2 mg every 2 – 4 hours until diarrhoea free for 12 hours) and appropriate rehydration.	Interrupt
	3	Interrupt and give appropriate rehydration, monitor electrolyte balance and renal function until resolution to Grade ≤ 1; restart at reduced dose.	Interrupt
	4	Discontinue treatment	
Rash	1	No intervention	None
	2	Any of the following: minocycline ^a , topical tetracycline or clindamycin, topical silver sulfadiazine, diphenhydramine, oral prednisone (short course)	None**
	3		Hold until recovery to ≤ grade 2, and then restart the dose.
	4	Discontinue treatment	
Other toxicity	≥ 2 prolonged clinically significant toxicity	Treatment as appropriate	Hold until recovery to ≤ grade 1, and then restart at reduced dose.

* If no recovery after 14 days of holding drug, patients should be discontinued from the study

** If dose has been previously held for grade 2 rash or diarrhoea, and grade 2 symptoms recur, or if the patient finds the symptoms unacceptable, hold dose until recovery to ≤ grade 1 and then reduce the dose.

^a Recommended dose: 200 mg p.o. b.i.d. (loading dose), followed by 100 mg p.o. b.i.d. for 7-10 days.

Rash:

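### Section 6.1's general dose-reduction rule and Table 4's discontinuation rows give different instructions for keratitis Grade 3 or worse, diarrhoea Grade 4 and rash Grade 4, and no sentence says which governs

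*Protocol*

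**What the plan says.** Protocol section 6.1 contains two sets of instructions for toxicity.

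**The prose** (Dose Modifications, Interruptions and Delays) is triggered by toxicity that optimal supportive care does not control or that the patient does not tolerate. Diarrhoea and rash are named only as examples. In that event, "regardless of severity, the daily dose of erlotinib will be decreased to 100 mg/day". Within two weeks of a reduction the toxicity must fall by at least one grade and be at Grade 2 or lower. The eye has a stricter target: "any ocular toxicity must improve to NCI-CTC Grade 1), or a further dose reduction to 50 mg/day will be required". The ladder has one stop rule: "Patients who cannot tolerate a dose reduction to 50 mg/day will be permanently discontinued from the study". A pause is optional: "Dosing may be interrupted for a maximum of 2 weeks if clinically indicated".

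**Table 4** is titled "Guidelines for management of erlotinib-related toxic effects". For keratitis of Grade 3 or worse it says "Discontinue treatment and seek ophthalmological advice". The Grade 4 rows for diarrhoea and for rash also say to discontinue. For Grade 2 keratitis it says "Hold until recovery, and then restart at reduced dose", with a footnote: "If no recovery after 14 days of holding drug, patients should be discontinued from the study".

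**Elsewhere**, section 6.1 has erlotinib stopped once interstitial lung disease (ILD) is diagnosed. Section 7.3 requires permanent discontinuation for gastrointestinal perforation, and interruption or discontinuation for acute or worsening ocular disorders. Table 6 and SAP 5.2.2 class as Major both a departure from the dose-reduction schedule and a failure to stop treatment once withdrawal criteria are met.

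**The concern.** For the three Table 4 cells that call for discontinuation, the prose and the table prescribe different actions for the same patient whenever the toxicity is uncontrolled or not tolerated. The prose is phrased as mandatory, covers every severity, and sets its own recovery target for the eye, so it cannot be confined to rash and diarrhoea.

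A site that works from the dose-modification paragraphs and Table 3 alone finds a complete algorithm that never says to stop for Grade 3 keratitis, Grade 4 diarrhoea or Grade 4 rash. The error runs in the less safe direction: section 7.3 itself lists keratitis among the risk factors for corneal perforation and ulceration. There is a smaller consequence for deviation coding, because either action could arguably be coded as a Major deviation, depending on which text is taken to govern.

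**Working it through.** The plan states no figure on this point, so the check is a comparison of texts. The short sum at the end is illustrative only.

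**1. Side by side.** Take a patient on 150 mg/day whose toxicity is uncontrolled or not tolerated.

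| Toxicity | Section 6.1 prose, read literally | Table 4 |
|---|---|---|
| Keratitis, Grade 3 or worse | 100 mg/day, then 50 mg/day if not Grade 1 within 2 weeks | Discontinue |
| Diarrhoea, Grade 4 | 100 mg/day, then 50 mg/day if not Grade 2 or better within 2 weeks | Discontinue |
| Rash, Grade 4 | 100 mg/day, then 50 mg/day if not Grade 2 or better within 2 weeks | Discontinue |
| Further dose levels | up to 2 | 0 |

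The severity phrase is attached to the first step, to 100 mg. The second step is conditional on inadequate improvement.

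**2. Search for a ranking sentence.**
- Section 3.1 refers dose reduction for toxicity to section 6.1, which holds both texts.
- The one pointer to Table 4 for a dose decision is in the rash paragraph. It concerns severe rash and leaves both stopping and reducing open.
- The two-week rule is repeated below Table 4, but under the rash heading, so the absence of a keratitis exception there adds little.
- Section 7.3 mentions neither Table 4 nor precedence, and the SAP gives no dose-modification rule.

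No sentence ranks the prose against the table.

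**3. Illustration of the gap.** Assume Grade 3 keratitis at 150 mg/day, full adherence and action on the day of onset, and count the first 28 days.
- Table 4: discontinue, 0 mg.
- Prose, 14-day hold and then 100 mg/day: 14 × 0 + 14 × 100 = 1,400 mg.
- Prose, no hold, not at Grade 1 by day 14: 14 × 100 + 14 × 50 = 2,100 mg.
- Prose, no hold, Grade 1 by day 14: 28 × 100 = 2,800 mg.
- Unreduced dose, for reference: 28 × 150 = 4,200 mg.

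These sums compare dose schedules, not harm, and the 28-day window is arbitrary. Nor is 1,400 mg a floor: reductions may be made at any time, so a patient could step to 50 mg/day, fail and stop sooner under the prose.

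**The case against.** The strongest reply is that the documents, read together, already give the answer.

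- Table 4 is specific to toxicity and grade, while the prose is a general default.
- Section 6.1 opens by limiting dosing to the period before progression or unacceptable toxicity, and section 4.6 lets the investigator withdraw a patient for an adverse event.
- The sentences that introduce the ladder are permissive.
- The severity phrase can be read as meaning that even mild toxicity qualifies for reduction if the patient cannot bear it.
- At its literal width the sentence would also override stopping for diagnosed ILD and for gastrointestinal perforation, which nobody can have intended.
- Table 6 makes failure to discontinue a Major deviation, which treats stop rules as binding.

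All of this stands as an argument about the sensible reading, and that reading favours Table 4. It does not remove the mandatory wording in "regardless of severity, the daily dose of erlotinib will be decreased to 100 mg/day" or the explicit ocular step in "any ocular toxicity must improve to NCI-CTC Grade 1), or a further dose reduction to 50 mg/day will be required". It also does not supply a ranking for a table headed "Guidelines for management of erlotinib-related toxic effects".

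A reader might infer more than the text supports, in three ways.

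- *That the prose is contrary to section 7.3.* Section 7.3 accepts interruption, so a hold followed by reduction is consistent with it. Only reduction without a hold departs from it.
- *That Grade 2 keratitis is also contradictory.* It is a difference of wording: the prose makes a hold optional and Table 4 directs one. Holding and then restarting at 100 mg satisfies both.
- *That the protocol compels continued treatment.* It does not; stopping for unacceptable toxicity always remains open.

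**Conclusion.** The point holds as a contradiction in wording across three Table 4 cells: keratitis Grade 3 or worse, diarrhoea Grade 4 and rash Grade 4. It applies when the toxicity is uncontrolled or not tolerated. In each, the literal prose leaves up to two further dose levels where Table 4 leaves none, and the prose is the less safe instruction.

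The practical size cannot be estimated. The documents give no rate for these events at these grades in this population, and exclusion criterion 5 removes patients with disorders that raise the risk of corneal lesions. The number affected among 30 may be zero. It would be tempting to infer harm to patients or bias in the results, but the documents support neither. The primary ITT analysis is unaffected, because membership rests on enrolment to the treatment phase and not on the dosing rule followed. Per-protocol membership could turn on which text governs, but any effect is unknown. The change is worth making because it is cheap and concerns when to stop a drug, not because the trial's conclusions depend on it.

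**What to change.** Add one sentence after the reduction ladder in section 6.1:

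> Where Table 4 says to discontinue treatment (keratitis Grade 3 or worse, diarrhoea Grade 4, rash Grade 4), or where this protocol otherwise requires discontinuation (diagnosed ILD, gastrointestinal perforation), erlotinib is discontinued and the reduction schedule does not apply.

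Add a cross-reference under Table 6 and in SAP 5.2.2, so that dosing, dose-reduction and discontinuation deviations are judged against this rule.

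The sentence should cover all the discontinuation rows. Exempting keratitis alone would leave the same conflict for diarrhoea and rash, and could suggest that the ladder does apply to them at Grade 4. Leave the Grade 2 keratitis row as it is.

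The cost is protocol and SAP wording, with no change to sample size, visits or the primary analysis.

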Skin rash or dermatosis (Grade 1 – 2) has been observed during the first several days of treatment with erlotinib in more than 50% and has been observed to diminish in severity despite continued treatment in many patients. In some patients, particularly when a superimposed infection is suspected, this rash appeared to improve with topical and oral antibiotics. In general, rash manifests as a mild or moderate erythematous and papulopustular rash, which may occur, or worsen, in sun exposed areas. For patients who are exposed to sun, protective clothing, and/or use of sun screen (e.g. mineral-containing) may be advisable. In patients with severe rash, treatment may need to be discontinued or the dose reduced (see table 4 below).

In the event of a rash, dose can be re-escalated when rash is \leq grade 2. Within 2 weeks following a dose reduction, erlotinib related toxicity must improve by at least one NCI-CTC grade and be NCI-CTC Grade 2, or further dose reduction by one level will be required. Dosing may be interrupted for a maximum of 2 weeks if clinically indicated and if the toxicity is not controlled by optimal supportive medication. Once a patient has had a dose reduction for toxicity, the dose will not be re-escalated except in the case of erlotinib related rash.

Stevens-Johnson syndrome

Very rare cases suggestive of Stevens-Johnson syndrome/Toxic epidermal necrolysis have been reported, which in some cases were fatal - see section 4.8 of SPC (30). Erlotinib treatment should be interrupted or discontinued if the patient develops severe bullous, blistering or exfoliating conditions.

Interstitial Lung Disease (ILD)

In patients who develop acute onset of new and/or progressive unexplained pulmonary symptoms such as dyspnoea, cough and fever, erlotinib therapy should be interrupted pending diagnostic evaluation. If ILD is diagnosed, Erlotinib should be discontinued and appropriate treatment initiated as necessary - see section 4.8 of the SPC (30). If ILD is excluded, re-medication is considered at the same dose.

Missed doses:

Doses should be taken at the same time each day. If the patient vomits after ingesting the tablets, the dose will be replaced only if the tablets can actually be seen and counted. A missed dose normally taken in the morning can be taken any time during the same day. Patients will be asked to report any missed doses to study site personnel.

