8.2.3 Types of Analyses

8.2.3.1. Efficacy Analysis

Efficacy analysis will be based on the intent-to-treat and per-protocol population. The ITT analysis will be considered as the primary analysis.

8.2.3.1.1. Intent to treat population:

Intention to treat population will be defined as all subjects who are enrolled to the treatment phase of the study, regardless if they completed treatment.

8.2.3.1.2. Per-protocol population:

Per protocol population will include all subjects enrolled in the treatment phase of the study without major protocol violations. The protocol violations and corresponding impact are listed below.

Table 6 – Categories of protocol deviations

Category	Impact
Assessment not performed	Minor/Major
Deviations from the dosing of the IPs	Major
Inconsistency with inclusion/exclusion criteria	Major
Non-compliance with the dose reduction schedule	Major
Prohibited concomitant medication	Major
Treatment not discontinued after withdrawal criteria is met	Major
Visit dates not per protocol	Minor

8.2.3.2. Safety Population:

All patients who received at least one dose of study medication will be included in the safety population.

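### Rash that has not improved two weeks after a dose reduction both requires a further reduction and permits re-escalation, with no stated precedence

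*Protocol*

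**What the plan says.** Three places in Protocol Section 6.1 govern dosing for rash.

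- **Dose modification text.** A toxicity that is uncontrolled by supportive care, or "not tolerated due to any reason, regardless of severity, the daily dose of erlotinib will be decreased to 100 mg/day". So a Grade 2 rash can lead to a reduction. Within two weeks of it, "erlotinib related toxicity must improve by at least one NCI-CTC grade and be NCI-CTC Grade 2 or better", "or a further dose reduction to 50 mg/day will be required". Re-escalation after a reduction is barred except for rash, where "In the event of a rash, dose can be re-escalated when rash is NCI-CTC Grade 2".
- **Table 4.** The dose entry for Grade 2 rash is no modification, subject to footnote **. The footnote applies if the dose was held before for Grade 2 rash or diarrhoea and Grade 2 symptoms return, or if the patient finds the symptoms unacceptable. The action is then to "hold dose until recovery to ≤ grade 1 and then reduce the dose". For Grade 3 rash the entry is "Hold until recovery to ≤ grade 2, and then restart the dose".
- **Rash paragraph.** It repeats the two-week test, with a further reduction of one level if the test fails. Immediately before that it permits re-escalation at Grade 2 or lower. It also says "In patients with severe rash, treatment may need to be discontinued or the dose reduced" and points to Table 4.

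On the analysis side, Table 6 (Protocol Section 8.2.3.1.2) classes "Non-compliance with the dose reduction schedule" as a major deviation, which removes a patient from the per-protocol population. SAP Section 5.2.2 has the same table.

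**The concern.** The two-week test looks at change in grade, while the re-escalation rule looks only at current grade. A patient whose rash has not changed can fail the first and satisfy the second on the same day. Section 6.1 names rash as one of two major side effects of the drug, and about nine centres take part (Protocol Section 3.2), so sites may settle the conflict differently.

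Two things are at stake. Delivered dose, which is summarised per day and cumulatively (Protocol Section 8.2.4, SAP Table 22), could depend on which sentence a site applied. And a deviation from the reduction schedule cannot be judged the same way every time if the schedule gives more than one answer. That bears on the per-protocol analyses, including the per-protocol ORR in SAP Table 11.

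**Working it through.** No figure in the plan needs reproducing; the check is to apply the rules as written. Let G0 be the rash grade at the reduction and G1 the grade two weeks later.

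- Further reduction is required unless G0 − G1 ≥ 1 **and** G1 ≤ 2 (dose modification text; repeated in the Rash paragraph).
- Re-escalation is permitted if G1 = 2 (dose modification text) or G1 ≤ 2 (Rash paragraph). Neither place adds an improvement condition.
- The Table 4 entry follows from G1 and, at Grade 2, from footnote **.

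| G0 → G1 | G0 − G1 | Further reduction | Re-escalation | Table 4 at G1 |
|---|---|---|---|---|
| 2 → 2 | 0 | required | permitted in both places | no change; hold to ≤ Grade 1, then reduce, if footnote ** applies |
| 1 → 1 | 0 | required | permitted in the Rash paragraph | no change |
| 3 → 2 | 1 | not required | permitted in both places | no change; hold to ≤ Grade 1, then reduce, if footnote ** applies |
| 2 → 1 | 1 | not required | permitted in the Rash paragraph | no change |
| 3 → 1 | 2 | not required | permitted in the Rash paragraph | no change |
| 3 → 3 | 0 | required | not permitted | hold |

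**Grade 2 that stays Grade 2.** The improvement is 2 − 2 = 0, so the test fails and a further reduction is required. The grade is 2, so re-escalation is permitted. Footnote ** depends on two yes/no conditions (earlier hold with recurrence; unacceptable symptoms), which gives 2 × 2 = 4 cases. Required reduction and permitted re-escalation coincide in 4 of 4. The footnote's hold joins them in 3 of 4; in the fourth, Table 4 says no change. These are logical cases, not proportions of patients.

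**Other paths.** Persistent Grade 1 meets the same clash under the Rash paragraph. Grade 3 falling to Grade 2 passes the two-week test, so the clash arises only where footnote ** asks for a hold and reduction while the text permits re-escalation. Grade 2 or 3 falling to Grade 1 meets no clash.

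**Symbol.** The dose modification text prints a bare Grade 2 where the Rash paragraph has ≤ Grade 2. That may be a sign lost in text extraction and is not counted as an error. Grade 2 satisfies both versions.

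**Grade 3 restart.** Table 4 specifies a reduced dose on restart for Grade 2 keratitis, Grade 3 diarrhoea and the other-toxicity row. For Grade 3 rash it names no level.

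**The case against.** The strongest reply is that the further reduction is an obligation and re-escalation only a permission. A site that reduces breaches nothing, whereas a site that re-escalates an unimproved patient breaches the mandatory sentence. Re-escalation would then be optional once the two-week test is passed. This is a workable reading, and it rules out saying that two sites moving in opposite directions would be equally compliant. But the protocol does not state it. The rash sentence is itself a specific exception to the general ban on re-escalation and could as well be read to govern. Nor does the reply explain Table 4's default of no change for Grade 2.

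A second reply is that a patient on the footnote ** route is held to Grade 1 or less before reducing, so Grade 2 two weeks later is a relapse and not persistence. That is fair, but the test fails on either reference grade: 2 − 2 = 0 from the grade that led to the reduction, or 1 − 2 = −1 from Grade 1 at restart. The clash remains.

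Three inferences a reader might draw should be set aside:

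- That persistent Grade 2 rash always triggers a hold as well. It does so only when a footnote condition is met, and that hold ends in a reduction, the same direction as the two-week rule.
- That the reduction cancels itself because the re-escalation condition is already met at restart. A permission cancels nothing, and having a rash exception is a clinical choice the protocol states openly.
- That the Grade 3 entries contradict each other. The Rash paragraph says only what may be needed, and the rows specifying a reduced dose concern other toxicities. The restart level is unstated, which is an ambiguity.

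**Conclusion.** The conflict is real and rests on the printed rules alone. For rash unimproved two weeks after a reduction, Section 6.1 requires a further reduction and permits re-escalation without ranking the two, and Table 4 adds a third answer for Grade 2. The restart level after Grade 3 rash is a lesser gap.

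The size cannot be given as a count. The Rash paragraph reports Grade 1–2 rash early in treatment in more than 50% of patients, and a reader might turn this into 0.50 × 30 = 15, hence more than 15 of the 30 planned. That figure counts any early rash, for which Table 4's default is no dose change, and the same paragraph says rash lessens in many patients on continued treatment. It is also not true that every patient reduced for rash meets the conflict, since most improving paths avoid it. Those affected are mainly patients whose rash does not improve after a reduction or who meet footnote **, and their number is not stated.

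For the analysis, the per-protocol status of those patients cannot be decided consistently. A reader might infer that the main ORR result is compromised. The documents do not support that: the intention-to-treat analysis is primary, its membership does not depend on dosing compliance, and no hypothesis is tested (Protocol Sections 8.2.2 and 8.2.3.1).

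**What to change.** The sponsor should reconcile the dose modification text, Table 4 with footnote **, and the Rash paragraph into one consistent rule set for rash. It should say which rule prevails when more than one applies, and state the dose level at which treatment restarts after Grade 3 rash. Protocol Table 6 and the matching table in SAP Section 5.2.2 should then refer to that rule set as the standard for judging this deviation. Which clinical rule to adopt, and whether it turns on current grade, change in grade or both, is for the sponsor to decide.

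The cost is a wording change in one protocol section, a cross-reference in two tables and a short notice to sites. No extra patients or procedures are needed.

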6.4 Blinding and Unblinding

Not applicable, study is on open label, single arm trial.

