Diarrhoea has occurred in patients on erlotinib, and moderate or severe diarrhoea should be treated with loperamide. In some cases, dose reduction may be necessary. In the event of severe or persistent diarrhoea, nausea, anorexia, or vomiting associated with dehydration, erlotinib therapy should be interrupted and appropriate measures should be taken to treat the dehydration. There have been rare reports of hypokalaemia and renal failure (including fatalities). Some reports of renal failure were secondary to severe dehydration due to diarrhoea, vomiting and/or anorexia while others were confounded by concomitant chemotherapy. In more severe or persistent cases of diarrhoea, or cases leading to dehydration, particularly in groups of patients with aggravating risk factors (concomitant medications, symptoms or diseases or other predisposing conditions including advanced age), erlotinib therapy should be interrupted and appropriate measures should be taken to intensively rehydrate the patients intravenously. In addition, renal function and serum electrolytes including potassium should be monitored in patients at risk of dehydration.

Hepatitis, Hepatic Failure

Rare cases of hepatic failure (including fatalities) have been reported during use of erlotinib. Confounding factors have included pre-existing liver disease or concomitant hepatotoxic medications. Therefore, in such patients, periodic liver function testing should be considered. Erlotinib dosing should be interrupted if changes in liver function are severe.

Gastrointestinal perforation

Patients receiving erlotinib are at increased risk of developing gastrointestinal perforation, which was observed uncommonly (including some cases with a fatal outcome). Patients receiving concomitant anti-angiogenic agents, corticosteroids, non-steroidal anti-inflammatory drugs (NSAIDs), and/or taxane based chemotherapy, or who have prior history of peptic ulceration or diverticular disease are at increased risk. Erlotinib should be permanently discontinued in patients who develop gastrointestinal perforation).

Bullous and exfoliative skin disorders

Bullous, blistering and exfoliative skin conditions have been reported, including very rare cases suggestive of Stevens-Johnson syndrome/toxic epidermal necrolysis, which in some cases were fatal. Erlotinib treatment should be interrupted or discontinued if the patient develops severe bullous, blistering or exfoliating conditions.

Ocular Disorders

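### For Grade 2 diarrhoea, protocol Table 4 interrupts erlotinib without condition while sections 6.1 and 7.3 make interruption conditional, and no text says which governs

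*Protocol*

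**What the plan says.** Four places in the protocol bear on this, and one in the SAP.

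- **Section 6.1, Table 4, Grade 2 diarrhoea.** The management cell reads "Loperamide (4 mg at first onset, followed by 2 mg every 2 – 4 hours until diarrhoea free for 12 hours) and appropriate rehydration". The dose-modification cell holds the single word *Interrupt*. The row gives no condition for the hold, no recovery threshold and no restart dose. The Grade 3 row below it does give these: "Interrupt and give appropriate rehydration, monitor electrolyte balance and renal function until resolution to Grade" 1 or lower, then resumption at a lower dose.
- **Table 4 footnotes.** The single-asterisk note, attached to the dose-modification column heading, takes patients off study if they have not recovered after 14 days of holding. The double-asterisk note covers recurrence of Grade 2 rash or diarrhoea after an earlier hold, and symptoms the patient finds unacceptable. Its marker appears only in the Grade 2 rash cell.
- **Section 6.1, running text.** "Dosing may be interrupted for a maximum of 2 weeks if clinically indicated and if the toxicity is not controlled by optimal supportive medication". Separately, a reduction to 100 mg/day is required for toxicity on this wording: "not controlled by optimal supportive care, or not tolerated due to any reason, regardless of severity, the daily dose of erlotinib will be decreased".
- **Section 7.3.** "moderate or severe diarrhoea should be treated with loperamide. In some cases, dose reduction may be necessary". On holding drug: "In the event of severe or persistent diarrhoea, nausea, anorexia, or vomiting associated with dehydration, erlotinib therapy should be interrupted". A later sentence in the same paragraph extends interruption to more severe or persistent diarrhoea, or diarrhoea that leads to dehydration.
- **Section 8.2.3.1.2, Table 6, repeated in SAP section 5.2.2.** Deviations in study-drug dosing are rated Major, with no Minor option. So is "Non-compliance with the dose reduction schedule". Patients with a Major deviation leave the per-protocol population.

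**The concern.** Section 6.1 names diarrhoea as one of the two major side effects of erlotinib, and the supportive-care text puts its frequency at about 50% of patients. With about nine centres, two investigators facing the same Grade 2 patient could do opposite things, one holding the drug and one continuing it, each with protocol text in support.

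The first consequence is inconsistent management and delivered dose. The second is statistical and less certain. If whoever classifies deviations reads Table 4 as binding, a patient who continued drug has a dosing deviation. If they read the section 6.1 condition as binding, a patient who was held while controlled has one. Table 6 allows no grade below Major for either.

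**Working it through.** The conflict is between texts, and no planned figure depends on it, so there is no stated result to reproduce. The check is whether any course of action satisfies every text.

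**Inputs.** Table 4 (Grade 2 diarrhoea row and both footnotes), the running text of section 6.1, section 7.3, and Table 6. Section 7.3 speaks of moderate diarrhoea. I read moderate as Grade 2, as Table 5 labels it, although Table 5 formally covers only events not listed in CTCAE.

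**Case A: Grade 2, controlled on loperamide, no dehydration, not persistent.**

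| Action | Table 4 | Section 6.1 text | Section 7.3 |
|---|---|---|---|
| Continue dosing | Departs: the row says interrupt | Fits: the condition for interrupting is not met | Fits: loperamide given, no trigger for interruption |
| Hold dosing | Fits | Departs: supportive medication has controlled the toxicity | Not called for |

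Neither action fits all the texts.

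**Case B: Grade 2, not controlled on loperamide.** Table 4 interrupts. Section 6.1 permits a hold if clinically indicated and requires a reduction. Section 7.3 allows for a reduction and reaches interruption if the diarrhoea persists. A hold followed by a reduced dose can be squared with all of them, so the contradiction is confined to Case A.

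**Restart after a first hold.** The single-asterisk footnote limits how long a hold may last without recovery. The double-asterisk footnote covers a second episode and unacceptable symptoms. Neither says at what grade, or at what dose, a patient resumes after a first Grade 2 diarrhoea hold. Where the toxicity was uncontrolled or not tolerated, the section 6.1 reduction rule supplies a dose. In Case A nothing does.

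**Number of patients.** At the stated frequency, 0.5 × 30 = 15 patients would have diarrhoea of any grade. Case A is a subset: those with Grade 2 diarrhoea that loperamide controls. The documents give neither the split by grade nor the control rate. On the protocol's own frequency the expected number lies somewhere between 0 and about 15, and nothing narrows it.

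**The case against.** The strongest defence is that Table 4 is titled as guidelines and sits under a supportive-care heading, so it could yield to the general rule in section 6.1. Alternatively, it could be the specific case that the general rule leaves to be filled in. Either reading would settle the matter, but they settle it in opposite directions and the protocol adopts neither. The footnotes do narrow the restart gap, as shown above, but do not close it.

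Other objections limit the point, and they stand. A reader might infer more than the documents support in four ways.

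- *That three texts give three different instructions.* Section 6.1 and section 7.3 differ in wording but largely fit each other. The outlier is the unconditional entry in Table 4.
- *That Grade 3 is contradictory too, because the Table 4 row omits loperamide while section 7.3 calls for it.* Silence is not a contrary instruction. The paragraph above the table recommends loperamide without a grade limit, and section 4.5 allows anti-diarrhoeals throughout. Both Table 4 and the later sentence in section 7.3 interrupt more severe cases. Section 7.3 says only that reduction may sometimes be needed, so following the Grade 3 row does not breach it. Loperamide is also not the study drug, so its use cannot be a study-drug dosing deviation.
- *That affected patients are Major deviations as a matter of fact.* No text says that departing from Table 4 counts as a dosing deviation. The line "Non-compliance with the dose reduction schedule" reads most naturally as the 150/100/50 mg/day steps of Table 3, whereas the Grade 2 dispute is about interruption. Only the broader dosing category in Table 6 could apply, and applying it is an inference.
- *That the per-protocol response rate loses a calculable amount of precision.* That would require assuming the share with Grade 2 or higher diarrhoea and then excluding all of them. The documents support neither step.

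**Conclusion.** The point holds for Grade 2 diarrhoea. A patient controlled on loperamide cannot be managed in line with Table 4, section 6.1 and section 7.3 together, none is said to govern, and restart after a first hold is not stated.

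The conflict between Table 4 and the section 6.1 text stands without any mapping of severity terms. Bringing in section 7.3 rests on reading moderate as Grade 2. The point also assumes that the interrupt entry belongs to the Grade 2 row; the Grade 2 and Grade 3 rows each carry their own entry, which supports this.

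The analytic effect is possible rather than established, is confined to per-protocol membership, and cannot be sized from the documents. Section 8.2.3.1 and SAP section 5.3.9 make ITT the primary analysis and section 8.2.2 plans no hypothesis test, so the primary response-rate denominator does not change. This is an inconsistency worth correcting because it concerns a common toxicity, but it is not a threat to the primary result.

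**What to change.** The sponsor's clinical team should reconcile Table 4, the running text of section 6.1 and section 7.3 into one instruction for Grade 2 diarrhoea. It should say whether drug is held, on what condition, and how dosing restarts. The content is theirs to choose. The protocol should then state which text governs, and Table 6 and SAP section 5.2.2 should refer to it. The deviation rule should add that following either of the current texts is not counted as a Major deviation.

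The cost is wording in three places in the protocol, plus a line with Table 6 and one in SAP section 5.2.2, with the ethics submission that section 12 requires for protocol changes. No new data are needed. If dosing has already finished, the deviation-classification line can still be settled before the per-protocol population is fixed.
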